7. ASSESSMENTS

Every effort should be made to ensure that the protocol-required tests and procedures are completed as described. However, it is anticipated that from time to time there may be circumstances, outside of the control of the investigator that may make it unfeasible to perform the test. In these cases the investigator will take all steps necessary to ensure the safety and well-being of the patient. When a protocol-required test cannot be performed, the investigator will document the reason for this and any corrective and preventive actions that he or she has taken to ensure that normal processes are adhered to as soon as possible. The study team will be informed of these incidents in a timely fashion.

7.1. Safety Assessment

Safety assessments will include collection of AEs, vital signs and physical examination, electrocardiogram (12-lead ECG), laboratory assessments, including pregnancy tests, and verification of concomitant treatments.

7.1.1. Pregnancy Testing

PF-05082566 has not been characterized for reproductive toxicology.

Toxicological studies indicated that mogamulizumab has no potential for embryo-fetal lethality, teratogenicity, or fetal growth retardation in animals. However no data are available in humans. The current mogamulizumab IB version^[18] contains a full description of non-clinical reproductive and developmental toxicology.

See [Section 8.10](#) for exposure during pregnancy.

For female patients of childbearing potential, a serum or urine pregnancy test, with sensitivity of at least 25 mIU/mL, will be performed on 2 occasions prior to starting study therapy (ie, once at the start of screening and once at the baseline visit, immediately before investigational product administration). Following a negative pregnancy result at screening, appropriate contraception must be commenced and a further negative pregnancy result will then be required at the baseline visit before the patient may receive the investigational product. Pregnancy tests will also be routinely repeated at every cycle (ie, on Day 1) during the active treatment period, at the End of Treatment visit, and additionally whenever 1 menstrual cycle is missed or when potential pregnancy is otherwise suspected. In the case of a positive hCG test, the patient will be withdrawn from study medication but may remain in the study.

Additional pregnancy tests may also be undertaken if requested by Institutional Review Boards (IRBs)/Ethic Committee (ECs) or if required by local regulations.

7.1.2. Adverse Events

Assessment of AEs will include the type, incidence, severity (graded by the National Cancer Institute Common Terminology Criteria for Adverse Events [NCI CTCAE] version 4.03), seriousness, and relatedness.

7.1.3. Laboratory Safety Assessment

Hematology, blood chemistry, coagulation, urinalysis, thyroid and other endocrine function tests will be drawn at the time points described in the Schedule of Activities ([Table 1](#)) and analysed at local laboratories. There is no need to repeat these tests on Cycle 1 Day 1 if screening assessment was performed within 7 days prior to that date.

Laboratory certifications and normal ranges with units must be provided to the Sponsor. Laboratory tests may be repeated also as clinically indicated.

Required tests are indicated in Table 10.

Table 10. Laboratory Safety Assessments

Hematology	Hemoglobin (Hb) Platelets (PLTs) White Blood Cells (WBCs) Absolute Neutrophils Absolute Lymphocytes Absolute Monocytes Absolute Eosinophils Absolute Basophils
-------------------	-------------------------------------------------------------------------------------------------------------------------------------------------------------------------------------

Table 10. Laboratory Safety Assessments

Chemistry	Alanine aminotransferase (ALT) Aspartate Aminotransferase (AST) Alkaline Phosphatase (ALP) Lactate Dehydrogenase (LDH) Sodium (Na) Potassium (K) Magnesium (Mg) Total Calcium (Ca) Phosphorus or Phosphate Total bilirubin*** Creatinine or creatinine clearance Albumin Total proteins Uric Acid BUN or Urea Immunoglobulin G Glucose (fasted)
Coagulation	Partial thromboplastin time (PTT) Prothrombin Time (PT) or International Normalized Ration (INR)
Urinalysis	Urine dipstick for urine protein. If positive collect 24-hrs and microscopic (Reflex Testing) Urine dipstick for urine blood. If positive collect a microscopic (Reflex Testing)
Hepatitis B and C Tests	Hepatitis B surface antigen, core antibody, and anti-hepatitis C. Other tests may be conducted per standard practice to confirm an active hepatitis infection.
Thyroid and other Endocrine Function Tests	Triiodothyronine (T3), Free-Thyroxine (FT4), Thyroid-Stimulating Hormone (TSH). In the presence of clinical suspicion of hypopituitarism or hypoadrenalinism, laboratory testing should include one or more of the following: Adrenocorticotrophic hormone (ACTH), and cortisol levels (before and 30- 60 minutes after corticotrophin stimulation).

*** For Hy's law potential cases, in addition to repeating AST and ALT, laboratory tests should include albumin, creatine kinase, total bilirubin, direct and indirect bilirubin, gamma-glutamyl transferase, PT/INR, and ALP.

7.1.4. Vital Signs and Physical Examination (PE)

Patients will have a physical exam (PE) that will include major body systems, weight, vital signs (blood pressure and heart rate), assessment of ECOG performance status, and height; height will be measured at baseline only. Each assessment will be performed at the time points described in the SOA [Table 1](#).

7.1.5. Electrocardiogram (12-Lead)

ECG): Triplicate 12-lead (with a 10-second rhythm strip) tracing will be used for all ECGs. It is preferable that the machine used has a capacity to calculate the standard intervals automatically. At each time point (see [Table 1](#)), three consecutive ECGs will be performed at approximately 2 minutes apart to determine the mean QTcF interval.

If the mean QTcF is prolonged (>500 msec, ie, NCI CTC AE Grade ≥ 3), then the ECGs should be re-evaluated by a qualified person at the site for confirmation as soon as the finding is made, including verification that the machine reading is accurate. If manual reading verifies a QTcF of >500 msec, prior to concluding that an episode of prolongation of the QTcF interval is due to study drug and is considered clinically significant, immediate correction of potential precipitating factors (including change in patient clinical condition, electrolyte abnormalities, hypoxia and concomitant administration of drugs with the potential to prolong the QTcF interval) should be performed.

In addition, repeat ECGs should be immediately performed hourly for at least 3 hours until the QTcF interval falls below ≤ 470 msec (ie, inclusion criteria) or is recovered to ≤ 480 msec (ie, NCI CTC AE Grade ≤ 1). If QTcF interval reverts to less than ≤ 480 msec, and in the judgment of the investigator(s) and Sponsor is determined to be due to cause(s) other than study drug, treatment may be continued with regular ECG monitoring at the same dose level.

If in this timeframe the QTcF intervals remains above 500 msec the study drug will be held until the QTcF interval decreases to ≤ 500 msec (NCI CTC AE Grade ≤ 2). Patients will then re-start the study drug at the next lowest dose level according to Investigator's judgment therefore excluding that the event is considered clinically significant.

If the QTcF interval has still not decreased to <500 msec after 2-weeks off treatment or if at any time a patient has a QTcF interval >515 msec (considered clinically significant) or becomes symptomatic, the study treatment will be permanently discontinued.

Additional triplicate ECGs may be performed as clinically indicated.

If patient experiences a cardiac or neurologic AE (specifically syncope, dizziness, seizures, or stroke), ECGs (triplicate) should be obtained at the time of the event.

Pre-dose ECG assessments will be required for all patients, post-dose ECG assessments will be required only for patients in dose-finding cohorts (see [Table 1](#)).

Clinically significant abnormal findings in baseline ECGs will be recorded as medical history.

Clinically significant findings seen on the follow-up ECGs should be recorded as AEs.

When matched with PK sampling, the ECG must be carried out before each PK sample drawing such that the PK sample is collected at the nominal time (ie, the timing of the PK collections over rides the timing of the ECG collections).

7.2. Tumor Assessments

Tumor assessments will include all known or suspected disease sites. Imaging may include chest, abdomen and pelvis computed tomography (CT) or magnetic resonance imaging (MRI) scans; brain CT or MRI scan for patients with known or suspected brain metastases; bone scan and/or bone X-rays for patients with known or suspected bone metastases.

The same imaging technique used to characterize each identified and reported lesion at baseline will be employed in the following tumor assessments.

Anti-tumor activity will be assessed through radiological tumor assessments conducted at baseline, and on treatment every 8 weeks \pm 7 days starting from Cycle 1 Day 1 up to 1 year, then every 3 months (\pm 7 days) as specified in [Table 1](#). Timing should follow calendar days starting from C1D1 and should not be adjusted for treatment delays.

Follow up bone scans are required every 16 weeks (\pm 7 days) only if bone metastases are present at baseline and bone scan is used to follow bone lesions on treatment. Otherwise bone imaging is required only if new bone metastasis are suspected and at the time of confirmation of complete response for patients who have bone metastases at baseline. The same imaging technique used at baseline for bone lesions assessments should be used to assess the on treatment response to bones.

In addition, radiological tumor assessments will also be conducted whenever disease progression is suspected (eg, symptomatic deterioration), and at the time of EOT (if not done in the previous 8 weeks).

Note that a lesion biopsied while on study, or a lesion that is irradiated during the study should no longer count as a target lesion.

Assessment of response will be made using RECIST version 1.1 ([Appendix 2](#)) and also by irRC ([Appendix 3](#)).

If radiologic imaging shows progressive disease, tumor assessment should be repeated \geq 4 weeks later in order to confirm progressive disease with the option of continuing treatment per [Section 5.4.5](#) while awaiting radiologic confirmation of progression.

In this trial, patients may be treated after initial progression by RECIST criteria and/or irRC, and patient's tumors will be subsequently assessed. A patient who has initial progression may be assigned PR or CR at a later time point as long as the patient meets all criteria for PR or CR compared to the pretreatment tumor assessment. If CR or PR is subsequently confirmed with respect to baseline, the patient's overall assessment will be CR or PR regardless of early assessment of progressive disease.

In addition to on-study tumor response assessments, the history of responses to previous therapy will be collected. This will include information on prior regimens, including dosing and duration of administration, plus a description of the best response observed for each prior regimen.

All patients' files and radiologic images must be available for source verification and for potential peer review.

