4.1. Inclusion Criteria

Patients must meet all of the following inclusion criteria to be eligible for enrollment into the study:

1. Histological or cytological diagnosis of advanced/metastatic solid tumor malignancy. Dose Finding Cohorts: Tumor types will be limited to CRC, SCCHN, squamous NSCLC, bladder, or ovarian carcinomas which have progressed on standard therapy, or for which no standard therapy is available. Expansion Cohorts: Tumor types may include: Histological or cytological diagnosis of either advanced/metastatic CRC, bladder, ovarian, squamous esophageal, SCCHN, or squamous NSCLC. **NOTE:** Final determination of tumor types for expansion will be made based on emerging data from the dose-finding portion of the study or obtained from ongoing studies testing PF-05082566.
2. Measurable disease by RECIST version 1.1.
3. For Expansion Cohorts only: patients must have tumor accessible for biopsies (core needle biopsy or excision preferred). See [Section 3.1.7](#).
4. Age ≥ 18 years.
5. Eastern Cooperative Oncology Group (ECOG) performance status of 0 or 1.
6. Adequate bone marrow function, defined as follows:
 - absolute neutrophil count (ANC) $\geq 1.5 \times 10^9/L$ ($\geq 1,500/\mu L$);

- platelet (PLT) count $\geq 75 \times 10^9/L$ ($\geq 75,000/\mu L$);
- hemoglobin (Hb) $\geq 9.0 \text{ g/dL}$ ($\geq 5.6 \text{ mmol/L}$).

Patients must be transfusion independent (ie, no blood product transfusions for a period of at least 14 days prior to study registration).

7. Adequate renal function, including:

- serum creatinine $\leq 1.5 \times$ upper limit of normal (ULN); **OR**
- estimated creatinine clearance $\geq 60 \text{ mL/min}$ as calculated using the method standard for the institution.

8. Adequate liver function, including:

- Total serum bilirubin $\leq 1.5 \times$ ULN (unless the patient has documented Gilbert syndrome);
- Aspartate and Alanine aminotransferase (AST & ALT) $\leq 2.5 \times$ ULN;
- Alkaline phosphatase $\leq 2.5 \times$ ULN; ($\leq 5 \times$ ULN in case of bone metastasis).

9. Resolved acute effects of any prior therapy to baseline severity or CTCAE Grade ≤ 1 except for AEs not constituting a safety risk by investigator judgment.

10. Serum/urine pregnancy test (for females of childbearing potential) negative at screening and before the patient will receive the study treatment.

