All sites of disease must be assessed at baseline. Baseline assessments should be done as close as possible prior to study start. For an adequate baseline assessment, all required scans must be done within 28 days prior to treatment and all disease must be documented appropriately. If baseline assessment is inadequate, subsequent statuses generally should be indeterminate.

Target lesions

All measurable lesions up to a maximum of 2 lesions per organ, 5 lesions in total, representative of all involved organs, should be identified as target lesions at baseline. Target lesions should be selected on the basis of size (longest lesions) and suitability for accurate repeated measurements. Record the longest diameter for each lesion, except in the case of pathological lymph nodes for which the short axis should be recorded. The sum of the diameters (longest for non-nodal lesions, short axis for nodal lesions) for all target lesions at baseline will be the basis for comparison to assessments performed on study.

If two target lesions coalesce the measurement of the coalesced mass is used. If a large target lesion splits, the sum of the parts is used.

Measurements for target lesions that become small should continue to be recorded. If a target lesion becomes too small to measure, 0 mm should be recorded if the lesion is considered to have disappeared; otherwise a default value of 5 mm should be recorded.

NOTE: When nodal lesions decrease to <10 mm (normal), the actual measurement should still be recorded.

Non-target disease

All non-measurable disease is non-target. All measurable lesions not identified as target lesions are also included as non-target disease. Measurements are not required but rather assessments will be expressed as ABSENT, INDETERMINATE, PRESENT/NOT INCREASED, INCREASED. Multiple non-target lesions in one organ may be recorded as a single item on the case report form (eg, 'multiple enlarged pelvic lymph nodes' or 'multiple liver metastases').

OBJECTIVE RESPONSE STATUS AT EACH EVALUATION

Disease sites must be assessed using the same technique as baseline, including consistent administration of contrast and timing of scanning. If a change needs to be made the case must be discussed with the radiologist to determine if substitution is possible. If not, subsequent objective statuses are indeterminate.

Target disease

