- Complete Response (CR): Complete disappearance of all target lesions with the exception of nodal disease. All target nodes must decrease to normal size (short axis <10 mm). All target lesions must be assessed.
- Partial Response (PR): Greater than or equal to 30% decrease under baseline of the sum of diameters of all target measurable lesions. The short diameter is used in the sum for target nodes, while the longest diameter is used in the sum for all other target lesions. All target lesions must be assessed.
- Stable: Does not qualify for CR, PR or Progression. All target lesions must be assessed. Stable can follow PR only in the rare case that the sum increases by less than 20% from the nadir, but enough that a previously documented 30% decrease no longer holds.
- Objective Progression (PD): 20% increase in the sum of diameters of target measurable lesions above the smallest sum observed (over baseline if no decrease in the sum is observed during therapy), with a minimum absolute increase of 5 mm.
- Indeterminate. Progression has not been documented, and
 - One or more target measurable lesions have not been assessed;
or
 - Assessment methods used were inconsistent with those used at baseline;
or
 - One or more target lesions cannot be measured accurately (eg, poorly visible unless due to being too small to measure);
or
 - One or more target lesions were excised or irradiated and have not reappeared or increased.

Non-target disease

- CR: Disappearance of all non-target lesions and normalization of tumor marker levels. All lymph nodes must be 'normal' in size (<10 mm short axis).
- Non-CR/Non-PD: Persistence of any non-target lesions and/or tumor marker level above the normal limits.

- PD: Unequivocal progression of pre-existing lesions. Generally the overall tumor burden must increase sufficiently to merit discontinuation of therapy. In the presence of SD or PR in target disease, progression due to unequivocal increase in non-target disease should be rare.
- Indeterminate: Progression has not been determined and one or more non-target sites were not assessed or assessment methods were inconsistent with those used at baseline.

New Lesions

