6.2.2.2. Tumor Shrinkage from Baseline

Tumor shrinkage will be summarized as the percent change from baseline in target lesions (sum of longest diameter for non-nodal lesion and short axis for nodal lesion) per time point. It will be derived as:

- $((\text{Sum of target lesions at week XX} - \text{sum of target lesions at baseline}) / \text{sum of target lesions at baseline}) \times 100$.

The maximum reduction in target lesions from baseline will be derived across all the post-baseline assessments until documented disease progression, excluding assessments after start of subsequent anti-cancer therapy, as:

- Minimum of $((\text{sum of target lesions at week XX} - \text{sum of target lesions at baseline}) / \text{sum of target lesions at baseline}) \times 100$.

A waterfall plot of maximum percent reduction in the sum of longest diameter for non-nodal lesions and short axis for nodal lesions from baseline will be created. This plot will display the best percentage change from baseline in the sum of the diameter of all target lesions for each patient with measurable disease at baseline and at least one post-baseline assessment.

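### Section 7.2 and Appendix 2 treat a target lesion biopsied or irradiated on study differently, and no rule adjusts the baseline sum, so an unchanged tumour can show false shrinkage

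*Protocol*

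**What the plan says.** Protocol Section 7.2 says that "a lesion biopsied while on study, or a lesion that is irradiated during the study should no longer count as a target lesion". It does not say whether the lesion also leaves the baseline sum and the nadir, or whether it becomes a non-target lesion. The next sentence sends the reader to Appendices 2 and 3 for response assessment.

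Appendix 2 fixes the reference: the sum of diameters "for all target lesions at baseline will be the basis for comparison to assessments performed on study". CR, PR and Stable each carry the condition "All target lesions must be assessed". If progression has not been documented, target status is Indeterminate when "One or more target lesions were excised or irradiated and have not reappeared or increased". Needle biopsy is not in that list.

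Appendix 3 (irRECIST) also measures decrease from baseline. It has no rule for a lesion that stops being a target.

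SAP 6.2.2.2 says "Tumor shrinkage will be summarized as the percent change from baseline in target lesions" and divides by the baseline sum. It does not require the two sums to cover the same lesions. SAP 6.2.2.1 takes best overall response (BOR) from the reported responses.

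SAP 5.2.6 counts surgery recorded as resected or partially resected as new anti-cancer therapy. It exempts palliative radiotherapy and radiotherapy to a non-target lesion, but the wording leaves open whether these are two exemptions or one joint condition. Protocol 5.7.3 permits palliative radiotherapy and does not exclude target lesions.

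**The concern.** Two rules in the same protocol cover one event, an irradiated target lesion. One removes the lesion from the target set; the other withholds a CR, PR or Stable call. For a needle-biopsied target, Section 7.2 drops the lesion, while nothing in Appendix 2 stops it being measured.

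The Section 7.2 rule is also incomplete. If a lesion leaves the visit sum but stays in the baseline sum, the sum falls with no change in the tumour. The fall persists, so a scan at least 4 weeks later would confirm it rather than expose it.

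At stake are the waterfall plot and, less directly, BOR, ORR and PFS. Expansion cohorts are where preliminary activity is judged, and expansion patients must have tumour accessible for biopsy.

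**Working it through.** The plan states no figure on this point, so there is nothing to reproduce. The check applies its formula to an unchanged tumour.

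**Inputs**
- Target lesions (Appendix 2): "All measurable lesions up to a maximum of 2 lesions per organ, 5 lesions in total".
- PR (Appendix 2): "Greater than or equal to 30% decrease under baseline of the sum of diameters of all target measurable lesions".
- Progression in target lesions (Appendix 2): a 20% rise above the smallest sum, and at least 5 mm.
- Percent change (SAP 6.2.2.2): 100 × (visit sum − baseline sum) / baseline sum.
- Confirmed PR (SAP 6.2.2.1): two determinations at least 4 weeks apart.
- Scans every 8 weeks in the first year (Section 7.2).

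**Step 1. Lesion dropped from the visit sum only.** With k equal lesions and no change, the result is −100/k %. If the remaining lesions change by a fraction g, the visit sum is (1 − 1/k)(1 + g) of baseline. Setting this to 0.70 gives the PR limit. Setting it to 1.20 gives the 20% rise at the first scan after the drop, with baseline as nadir.

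| k | Change, tumour unchanged | g at the PR limit | g for a 20% rise |
|---|---|---|---|
| 2 | −50% | +40% | +140% |
| 3 | −33.3% | +5% | +80% |
| 4 | −25% | −6.7% | +60% |
| 5 | −20% | −12.5% | +50% |

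For k = 1 no target lesion remains to be summed, so I do not count that case.

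**Step 2. General condition.** If the dropped lesion is a share w of the baseline sum, the change is −100w %. The 30% limit is met when w ≥ 0.30. Example: 40 + 30 + 30 = 100 mm. Dropping the 40 mm lesion gives (60 − 100)/100 = −40%; dropping a 30 mm lesion gives −30%.

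**Step 3. Matched sums.** With the lesion removed from both sums, an unchanged tumour gives 0% for every k ≥ 2.

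**Step 4. The same scans under each rule.** Assume two equal targets, one irradiated before week 8 with palliative intent and not counted as new anti-cancer therapy; nothing changes until a new lesion appears at week 24. Assume also that Indeterminate in Appendix 2 is NE in the SAP.
- Visit sum only, with the all-targets-assessed condition set aside: −50% at weeks 8 and 16, a confirmed PR, and a PFS event at week 24.
- Matched sums: 0% at weeks 8 and 16, BOR of SD, and a PFS event at week 24.
- Appendix 2: Indeterminate at weeks 8 and 16. BOR is NE. Progression follows two inadequate assessments, so PFS is censored at first dose (SAP 5.2.11 and Table 3).

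**Step 5. Effect on ORR.** One false PR moves 0/40 (Clopper-Pearson 95% CI 0 to 8.8%) to 1/40 = 2.5% (0.1 to 13.2%). The documents give up to 40 expansion patients in total and no cohort sizes. If a cohort had 10, an assumption, 0/10 (0 to 30.8%) would become 1/10 = 10% (0.3 to 44.5%).

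**The case against.** The best defence is that the false shrinkage needs an inconsistent reading. If the lesion is still a target, it has not been properly assessed and status is Indeterminate. If it is no longer a target, it belongs in neither term of the formula. No text orders that it be counted at baseline and not at the visit. This is fair, but no text forbids it either, and Appendix 2 ties the reference to all baseline targets. A programmer following SAP 6.2.2.2 literally would produce the mismatch.

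Four stronger readings are tempting, and the documents do not support them.
- A reader might infer that the SAP formula itself creates false PRs in ORR. It feeds only the shrinkage summary and waterfall plot. A false PR also needs the reader to let Section 7.2 override the all-targets-assessed condition.
- A reader might infer that Appendix 2 makes the patient unevaluable and always a non-responder. Progression can still be called from target, non-target or new lesions, and a response confirmed before the lesion was altered still counts.
- A reader might infer that excision is a main route. Recorded resections are new anti-cancer therapy under SAP 5.2.6, so later scans do not enter BOR or maximum reduction. The same holds for non-palliative radiotherapy to a target.
- A reader might infer that nothing protects targets from biopsy. Inclusion criterion 3 points to Section 3.1.7, which is redacted, as are the biopsy footnotes. The Site Imaging Manual cited in Section 5.4.5 is not available. A selection rule may exist there.

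**Conclusion.** The point holds as a contradiction between Section 7.2 and Appendix 2 for irradiated targets, an unaligned rule for needle-biopsied ones, and a percent-change formula with no matched-lesion rule. False shrinkage of 20% to 50% arises if one of 5 to 2 equal lesions leaves the visit sum only. A reported PR further requires a lesion of at least 30% of the baseline sum and a reader who sets Appendix 2's condition aside. The main exposure is palliative radiotherapy to a target lesion, depending on how SAP 5.2.6 is read, and on-study biopsy. How often either will occur cannot be estimated from the documents.

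The severity is moderate. The primary endpoint is DLT, anti-tumour activity is secondary and summarised descriptively (Protocol 9.4), and no hypothesis is tested (SAP 5.1.1). A reader might rank this as a defect that must be corrected before the study can be interpreted; those facts do not support that.

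**What to change.** 1. Reconcile Section 7.2 with Appendices 2 and 3. State one rule covering target lesions irradiated, excised or needle-biopsied on study: either status is Indeterminate, or the lesion is removed from the visit, baseline and nadir sums alike. If removal is chosen, say what status applies when no target lesion remains.
2. In SAP 6.2.2.1 and 6.2.2.2, state that when a lesion is dropped under that rule, percent change uses the same lesion set at baseline, nadir and visit, and that no CR or PR may arise from removal of a lesion. Limit this to lesions dropped under the rule. Targets that are merely unassessed stay under the Appendix 2 Indeterminate rule; otherwise incomplete scans could yield responses.
3. In SAP 5.2.6, say whether palliative radiotherapy to a target lesion counts as new anti-cancer therapy.

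The cost is a few sentences in the protocol and SAP, with no extra scans or patients. The fix needs no instruction on which lesion to biopsy.
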